1 BACKGROUND

Plain English Summary:

Pleural mesothelioma (PM) is a cancer that affects the outside lining of the lung, caused by asbestos exposure. The UK has the highest rate of PM in the world, but despite recent treatment advances, average life expectancy remains under a year from diagnosis. Prompt diagnosis is therefore vital.

People with suspected PM usually require a biopsy of the lung lining to confirm the diagnosis, guide treatment and assist with compensation claims. However, some people need multiple biopsies which increases the risk of biopsy-related complications and prolongs the diagnostic process, causing additional stress and anxiety.

Some people with mesothelioma can deteriorate rapidly. A prolonged time to diagnosis could mean the time window in which someone is sufficiently strong to tolerate life-prolonging treatment is missed.

We believe doing additional tests on initial biopsies will increase the chance of diagnosing PM, avoiding repeat biopsies. This will shorten the period of anxious uncertainty and allow patients to start anti-cancer treatment sooner, improving their chances of survival. Reducing the number of biopsies will eliminate the risks associated with multiple procedures and free up space for other patients with suspected cancer, improving their diagnostic pathway as well.

The extra tests – while not genetic tests – look for markers of genetic changes that happen in PM. Genes are the building blocks in every cell of our bodies that make up who we are and how our bodies behave. Some genes work to stop tumours appearing and, if they do appear, stop them growing. PM tumours can stop these protective genes working or make them disappear, which allows the tumour to grow and spread inside the body. The markers affected in PM are called BAP1, p16 and MTAP and we can test biopsy samples for these. If all three have disappeared, then we can make a diagnosis of mesothelioma.

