Recent advances since TARGET have broadened the panel of tests available for PM biopsy samples. Homozygous deletion of the 9p21 locus is one of the most common genetic alterations in PM, affecting a cluster of tumour suppression genes that show diagnostic promise. These are BRCA-associated protein 1 (BAP1), p16 and methylthioadenosine phosphorylase (MTAP) [4, 5].

BAP1 is a tumour suppressor gene that is mutated in 40-60% of PM tumours, causing loss of BAP1 expression. A 2017 meta-analysis showed BAP1 loss had moderate diagnostic sensitivity (area under the curve of 0.72) with 100% specificity, making it an excellent 'rule-in' test for PM [6].

P16 deletion occurs in 80% of PM and is demonstrated using fluorescence in situ hybridisation (FISH). Diagnostic sensitivity of P16 FISH is 0.53, but 0.76 if combined with BAP1 testing [7].

FISH is not performed in all laboratories but immunohistochemical (IHC) staining is universally available. IHC expression of the protein product of the MTAP gene has been shown to be an accurate and reproducible surrogate marker for p16 FISH, with 78% sensitivity and 96% specificity for homozygous p16 deletion and is faster and cheaper to run [8]. When used in combination with BAP1, MTAP IHC has 100% specificity and 76.5% sensitivity for differentiating between malignant and benign mesothelial disease [6].

BAP1, p16 FISH and MTAP are used in some UK centres but are not universally available nor routinely recommended in current guidelines [9-11].

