3 OBJECTIVES AND OUTCOME MEASURES/ENDPOINTS

This research aims to answer the question: Could testing for BAP1, P16 FISH and MTAP IHC have removed the need for further invasive procedures in patients with suspected PM and an initial non-diagnostic biopsy?

We will address this question via the following objectives:

- Identify participants from the TARGET trial population (n=59)
- Extract historic biopsies (initial and repeat) from NHS pathology laboratories (n=129)
- Perform BAP1 and MTAP on all extracted biopsies. Where this fails to yield a diagnosis, perform additional p16 FISH.
- Identify patients for whom additional testing would have yielded a diagnosis, avoiding the need for further invasive tests (primary outcome).
- Investigate whether additional testing would have shortened the overall time to PM diagnosis (secondary outcome).
- Identify TARGET participants who ultimately received a clinico-radiological diagnosis, i.e. no tissue diagnosis was made, in whom additional testing would have provided a definitive diagnosis (sub-group analysis).

Primary and secondary outcomes, and outcome measures can be found in the study summary table.

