7.3 Data extraction

Baseline clinical information and follow up data from visits at 3, 6 and 12 months will be extracted from the trial database. Where this data is unavailable, it will be sought from medical records. Variables include:

- Baseline demographic data
- Asbestos exposure history
- Relevant medical background
- Biopsy dates and results
- Biopsy method
- Number of biopsies required for diagnosis
- Biopsy-related adverse events
- Histological diagnosis
- Whether diagnosis was tissue based or clinico-pathological.
- Time to diagnosis (from enrolment)
- Stage at diagnosis
- Number of MDT discussions

- MDT outcomes including ultimate MDT diagnosis and date of diagnosis
- Radiological images and reports used during diagnostic period
- Anti-cancer treatment received
- Healthcare utilisation
- Overall survival

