10 STATISTICS AND DATA ANALYSIS

The independent variable is the availability of BAP1, p16 FISH and MTAP testing (binary; available *vs* not available). The primary outcome is identification of malignancy on biopsy (binary; diagnostic *vs* non-diagnostic), with diagnosis defined as i) histopathological confirmation on standard testing or ii) histopathological features of PM with demonstrated BAP1, p16 or MTAP deletion or iii) Multi-disciplinary Team (MDT) diagnosis. It is assumed that confirmation of a malignant diagnosis stops the diagnostic pathway with no additional biopsies required. Any subsequent biopsies for these participants will not be included in the analysis, preventing double-counting. Secondary outcomes include total number of biopsies required, time to diagnosis, stage at diagnosis, number of MDT discussions, biopsy-associated costs, biopsy-related adverse events and survival. Potential confounding variables include age, sex, biopsy method and tumour histology and these will be adjusted for, when possible, in the analysis.

Outcome measures will be tabulated for standard and proposed pathways and compared using descriptive statistics (including the McNemar test). Univariable and multivariable logistic regression will look for an association between the availability of these tests and likelihood of a diagnostic biopsy. The relationship between secondary outcomes and availability of the tests will be evaluated using adjusted and unadjusted regression analyses and time to event analysis (cox proportional hazard model).

Sample Size:

Total number of patients: 59

Total histological samples for analysis: 129 (all participants had multiple biopsies)

REPLICA

IRAS ID 329574

Each participant will be assessed as a case (proposed pathway) and as an internal control (standard pathway) generating two groups of 59 = 118 records for inclusion in the study

Sample size is determined by the number recruited to the TARGET study which demonstrated diagnostic sensitivity (without these additional tests) of 30%. A sample size of 118 (59 in each arm) will allow detection of an increased diagnostic rate of 60% with 95% confidence intervals of +/- 8.8% (based on BAP1 loss prevalence of 60%).

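### The primary outcome lets added marker results only add diagnoses, and plans no check of those calls against the final MDT diagnosis, so a false positive would count as a gain

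*Protocol*

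**What the plan says.** The Trial Summary and Section 10 (Statistics and Data Analysis) define the primary outcome as identification of malignancy on biopsy, met by any of three routes: standard histopathology, "histopathological features of PM with demonstrated BAP1, p16 or MTAP deletion", or an MDT diagnosis. The routes are joined by the word or.

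Section 10 goes on: "It is assumed that confirmation of a malignant diagnosis stops the diagnostic pathway with no additional biopsies required". It adds: "Any subsequent biopsies for these participants will not be included in the analysis".

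Section 3 (Objectives) sets the order of testing: "Perform BAP1 and MTAP on all extracted biopsies. Where this fails to yield a diagnosis, perform additional p16 FISH". It also plans a sub-group analysis of participants whose final diagnosis was clinico-radiological, to see whether the added tests would have given a definitive diagnosis.

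Section 7.3 (Data extraction) lists "MDT outcomes including ultimate MDT diagnosis and date of diagnosis" among the variables to be collected. The Trial Summary says that the 12 months of follow-up are already complete.

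On test performance, Section 1 states that "BAP1 loss had moderate diagnostic sensitivity (area under the curve of 0.72) with 100% specificity". It gives 100% specificity for BAP1 combined with MTAP in separating malignant from benign mesothelial disease, and 96% for MTAP against homozygous p16 deletion. For p16 FISH it gives a sensitivity but no specificity.

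The Plain English Summary in Section 1 describes the rule differently: "If all three have disappeared, then we can make a diagnosis of mesothelioma".

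**The concern.** The cohort has suspected, not proven, malignancy. The study asks whether added tests on the first biopsy would have made further invasive procedures unnecessary, and the answer is yes only when the added call is right. As the outcome is written, nothing can mark a call as wrong:

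- The marker criterion can add a diagnosis and cannot remove one.
- The MDT criterion is an alternative route to a positive, so it cannot overturn a marker call.
- Later biopsies, which might contradict the call, leave the analysis once the call is made.
- The one planned analysis that uses the final diagnosis, the clinico-radiological sub-group, looks for further positives.

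A false-positive baseline sample would therefore raise the primary yield. It would also carry into the secondary outcomes on number of biopsies, time to diagnosis and cost, always in favour of the proposed pathway. The study is meant to inform national guidelines, so the reader needs to see how many of the gained diagnoses were borne out.

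**Working it through.** **The plan's own figures.** The protocol gives no figure for false positives. Its only precision figures are 95% half-widths for the yield, and they reproduce as 1.96 × √(p(1 − p)/n) with n = 118: 8.84 points at 60%, 8.27 at 70% and 7.22 at 80%, against the stated 8.8, 8.2 and 7.2. That n counts each of the 59 participants twice, which is a separate matter. With n = 59 the half-widths are 12.5, 11.7 and 10.2 points. They serve below only as a yardstick.

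**Direction of change.** Standard pathway: histopathology or MDT. Proposed pathway: histopathology or MDT or (PM features with marker loss). Every participant positive under the first is positive under the second, so all discordant pairs in the McNemar test run one way. With c such pairs the exact two-sided p-value is 2 × 0.5^c: c = 5 gives 0.0625 and c = 6 gives 0.031. The test does not ask whether those c calls were correct.

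**Expected false positives.** Let m be the number of participants without PM and s the per-participant specificity of the whole criterion. The expected count is m(1 − s), and the chance of at least one is 1 − s^m. The protocol gives neither m nor s. I take m from 10 to 41. The upper end treats the 30% standard diagnostic rate in Section 10 as if it were the share with PM: 0.30 × 59 = 17.7, about 18, and 59 − 18 = 41. Values of s below 100% are assumptions.

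| m (assumed) | s = 100% | s = 96% | s = 90% |
|---|---|---|---|
| 10 | 0 | 0.4 | 1.0 |
| 20 | 0 | 0.8 | 2.0 |
| 30 | 0 | 1.2 | 3.0 |
| 41 | 0 | 1.6 | 4.1 |

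As a share of 59, 0.4 is 0.7 points and 4.1 is 6.9 points. At s = 96% the chance of at least one false positive runs from 34% (m = 10) to 81% (m = 41).

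**Could false positives alone reach six?** From the binomial distribution, with m = 20 the chance of six or more is 0.01% at s = 96% and 0.4% at s = 92%. Only at the far corner, m = 41 and s = 90%, does it reach 22%.

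**Which steps are least supported.** On the cited 100% for BAP1 and for BAP1 with MTAP, the expected count at the immunohistochemistry step is 0. MTAP alone has 96%, but measured against p16 deletion and not against malignancy. p16 FISH has no cited specificity, and it is run only on samples where the first two markers did not give a diagnosis.

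**The two marker rules side by side.** Section 10 and the Trial Summary accept loss of any one marker. Section 3 runs p16 FISH only when BAP1 and MTAP have not given a diagnosis, which fits an any-one rule and leaves no planned route to an all-three result. The Plain English Summary speaks of all three. To see how far the rules differ, use the protocol's rates (BAP1 loss 40 to 60%; p16 53 to 80%) and assume independent BAP1 and p16 loss, with MTAP loss in 78% of p16 deletions:

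- Any one: 1 − 0.60 × 0.47 = 72% up to 1 − 0.40 × 0.20 = 92% of PM.
- All three: 0.40 × 0.53 × 0.78 = 17% up to 0.60 × 0.80 × 0.78 = 37% of PM.

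**The case against.** The other side has several good points.

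- Marker loss alone is never enough. The criterion also requires histopathological features of PM, so benign tissue with a chance marker loss does not qualify. This stands, although the protocol does not define those features and the baseline biopsies were first read as non-diagnostic.
- The protocol's own specificity figures for malignant against benign disease are 100%. This stands as a reason to expect few errors. It does not cover p16 FISH or MTAP alone, and the BAP1 with MTAP figure is for mesothelial disease, whereas this cohort has suspected pleural malignancy more broadly.
- A reader might put one or two false positives next to the six reclassified participants needed for p = 0.031 and infer that errors could produce the result. The documents do not support that: over most of the assumed range, six false positives are very unlikely.
- A reader might also infer that the study cannot tell useful diagnoses from wrong ones at all. That goes too far. The final diagnosis is extracted and will be linked to the marker results; what is missing is its use as a check.
- The all-three sentence could be taken for a second, competing endpoint. It is lay wording and is phrased as a sufficient condition, while the operative sections agree with one another. It is a conflict of wording.
- The protocol does not mention masking of slide readers. That silence may be filled in the analysis plan or laboratory procedures, and it is not part of this point.
- Tables and confidence intervals are commonly left to the analysis plan. That is fair for format. But the protocol itself fixes the one-way outcome, the stopping assumption and the removal of later biopsies.
- The MDT diagnosis is an imperfect reference and is itself one of the outcome criteria. This stands, and it is why the concordant-only yield should sit beside the defined yield and not replace it.

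**Conclusion.** The point holds as a gap in the definition of the primary outcome. Marker results can only add diagnoses, and apart from the clinico-radiological sub-group nothing planned checks the added calls against the final MDT diagnosis.

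The likely distortion is small: 0 participants on the protocol's cited 100% specificity, and about 0.4 to 4 of 59 (0.7 to 6.9 points of yield) if specificity is 90 to 96% and 10 to 41 participants do not have PM. All those inputs are assumed. Even the upper end is well below the anticipated rise from 30% to 60%, and below the 12.5-point half-width for 59 participants at a 60% yield. The value of the check is that it would show whether the biopsies counted as avoidable truly were. It should be made, but the study does not fail without it. The marker-rule wording is a minor point.

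**What to change.** In Section 10:

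1. Cross-classify each participant's baseline marker call against the ultimate 12-month MDT diagnosis. Report sensitivity and specificity with exact confidence intervals, and list the discordant cases. Exact intervals matter because the numbers are small: with 0 false positives among an assumed 20 non-malignant participants, the upper 95% limit for the false-positive rate is 1 − 0.025^(1/20) = 16.8%.
2. Report the gain in yield and the number of biopsies avoided counting only calls concordant with a final malignant diagnosis, beside the yield as now defined. State that the MDT reference is imperfect, so a discordant case is not automatically a marker error.
3. Reconcile the all-three sentence in the Plain English Summary with the any-one rule in the Trial Summary and Section 10 and with the testing order in Section 3, so that one marker rule is stated throughout.

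The cost is one table from data already being extracted and linked, plus a few lines of text. The downside is that the concordant-only yield may be lower by a few participants, and that it leans on a reference with errors of its own.

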	Objectives	Outcome Measures		
Primary	Identify patients for whom additional pathological testing would have yielded a definitive diagnosis on baseline biopsy, avoiding the need for further invasive tests	Identification of malignancy on biopsy (binary; diagnostic vs non-diagnostic) via: i) histopathological confirmation on standard testing or histopathological features of PM with demonstrated BAP1, p16 or MTAP deletion or iii) Multi-disciplinary Team (MDT) diagnosis		
Secondary	i) Investigate whether additional pathological testing would have shortened the overall time to diagnosis and ii) Investigate whether additional testing would have reduced costs	i) Total number of biopsies required ii) Time to diagnosis iii) Stage at diagnosis iv) Number of MDT discussions required v) Biopsy-associated costs vi) Biopsy-related adverse events		

in whom additional testing would have provided a definitive diagnosis

iv. FUNDING AND SUPPORT IN KIND

FUNDER(S) (Names and contact details of ALL organisations providing funding and/or support in kind for this trial)	FINANCIAL AND NON FINANCIALSUPPORT GIVEN
Southmead Hospital Charity [name] [contact]	Research grant
NBT NHS Trust	Salaries for [name], [name], [name], [name]
NIHR	Salary for [name]
University of Bristol	Salary for [name]
University of West of England	Salary for [name]

v. ROLE OF TRIAL SPONSOR AND FUNDER

The Sponsor and Funders have no role or remit in the study design, conduct, data analysis and interpretation, manuscript writing or dissemination of results.

vi. ROLES AND RESPONSIBILITIES OF TRIAL MANAGEMENT COMMITEES/GROUPS & INDIVIDUALS

Study management group:

Responsible for oversight of the study. It will monitor trial progress, ensure all practical details of the trial are progressing well and feed back to the sponsor. The study management group will be chaired by the CI and will include all members of the named research team. It will meet 4 times during the study period.

Patient and Public Involvement group:

IRAS ID 329574

This will involve a specialist nurse and trial co-ordinator communicating details of the trial progress to a group of mesothelioma patients and carers as the study progresses.

Study delivery group:

This involves the people responsible for retrieving histological samples and performing and reporting the pathological tests. They will ensure accuracy and reproducibility of the tests, and updating the investigators on progress.

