4 TRIAL DESIGN

Observational study using historic data and stored samples from a multi-centre randomised controlled trial (TARGET, ISRCTN 14024829), where each participant will act as a case (additional tests applied to stored samples) and an internal control (initial outcomes using standard testing only).

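### The primary outcome is called malignancy on biopsy but also counts an MDT diagnosis, with no tissue requirement, time point or pathway; scored over the whole pathway this dilutes the paired comparison

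*Protocol*

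**What the plan says.** Protocol Section 10 states: "The primary outcome is identification of malignancy on biopsy (binary; diagnostic *vs* non-diagnostic". It then lists three routes to a diagnostic result: i) standard histopathology, ii) histological features of pleural mesothelioma with loss of one of the three markers, "or iii) Multi-disciplinary Team (MDT) diagnosis". The primary outcome measure in the trial summary (section iii) gives the same third route.

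Four other places bear on it:

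- The primary objective in the trial summary: "Identify patients for whom additional pathological testing would have yielded a definitive diagnosis on baseline biopsy, avoiding the need for further invasive tests".
- The sub-group objective in Section 3, about participants "who ultimately received a clinico-radiological diagnosis, i.e. no tissue diagnosis was made". It asks in how many of them the additional tests would have given a definitive answer.
- Section 4, where each participant is also "an internal control (initial outcomes using standard testing only").
- Section 7.3, which extracts "MDT outcomes including ultimate MDT diagnosis and date of diagnosis" and, as a separate variable, whether the diagnosis rested on tissue.

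Section 10 names McNemar's test for comparing the two pathways. It also plans logistic regression of a diagnostic biopsy on test availability.

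**The concern.** An MDT diagnosis reached without tissue is not malignancy identified on biopsy, so the third route does not fit the outcome's own name. It also scores the same people in opposite ways. Section 3 treats participants with no tissue diagnosis as cases the new tests might rescue. Under the third route, the same participants can already be successes of the standard pathway.

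This matters because the design is paired. The two records of a participant differ only if the added tests change the classification, and McNemar's test uses only the pairs that differ. If the MDT diagnosis already makes the standard record diagnostic, a tissue diagnosis supplied by the markers changes nothing in the primary comparison. At stake is which participants are able to contribute to the primary result.

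**Working it through.** **The plan's own figures.** Section 10 plans on a standard rate of 30% and a proposed rate of 60% with a half-width of 8.8 points. The Wald formula 1.96 × √(p(1−p)/n) with p = 0.60 and n = 118 gives 8.84 points, so the stated figure reproduces. It says nothing about how the third route is scored.

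**Reading A: scored over the whole pathway.** A participant whose MDT diagnosis of malignancy had no tissue behind it is diagnostic under standard testing by route iii. The same historic diagnosis makes the participant diagnostic under the proposed pathway. The pair is concordant whatever the markers show.

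**Reading B: scored at the baseline biopsy.** TARGET eligibility (Section 6) required a non-diagnostic biopsy and an MDT decision to biopsy again. At that point no participant had a tissue or MDT diagnosis under standard testing, so route iii cannot apply there. It is inert or, if an MDT judgement is credited only once the new results are known, it can help only the proposed pathway.

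**Which reading the text supports.** The primary objective refers to the baseline biopsy, which points to B. The 30% standard rate points to A, because under B the standard rate would be zero by eligibility. The protocol does not settle it.

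**Size under reading A.** Inputs and assumptions:

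- 59 pairs (Section 10).
- Tissue-positive under standard: 0.30 × 59, about 18. Under proposed: 0.60 × 59, about 35. This takes the 30% and 60% as tissue-based rates and assumes no lost samples.
- Every standard tissue-positive stays positive, so discordance runs one way: 35 − 18 = 17 pairs, and 17/59 = 28.8 points.
- m = number of MDT-only malignant diagnoses among the 59 − 18 = 41 tissue-negative participants. The protocol does not give m; the values below are assumed.
- Exact two-sided McNemar with b one-way discordant pairs: p = 2 × 0.5^b. At least b = 6 is needed for p < 0.05 (b = 5 gives 0.0625, b = 6 gives 0.031).

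(a) Gains spread evenly over the 41: b = 17 × (1 − m/41), rounded.

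| m | Standard rate | b | Difference (points) | p |
|---|---|---|---|---|
| 0 | 18/59 = 30.5% | 17 | 28.8 | 0.00002 |
| 10 | 28/59 = 47.5% | 13 | 22.0 | 0.0002 |
| 20 | 38/59 = 64.4% | 9 | 15.3 | 0.004 |
| 30 | 48/59 = 81.4% | 5 | 8.5 | 0.06 |

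(b) Gains fall first among MDT-only participants: b = 17 − m, not below 0.

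| m | b | Difference (points) | p |
|---|---|---|---|
| 5 | 12 | 20.3 | 0.0005 |
| 10 | 7 | 11.9 | 0.016 |
| 15 | 2 | 3.4 | 0.50 |
| 17 or more | 0 | 0 | 1 |

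Series (b) is the extreme allocation and is shown only as the bound.

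**The case against.** A reader might infer that the outcome simply hides the benefit: that MDT-only participants are counted as standard-pathway successes and the planned 30-point gain could vanish. The documents do not support that as a statement of fact.

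- It holds under only one reading. Scored at the baseline biopsy, as the primary objective is worded, route iii gives the standard pathway no successes. This stands, and it is why the point is conditional. It does not rescue the definition, because under that reading route iii is inert or one-sided.
- Near-total loss needs both a large m and gains concentrated in MDT-only participants. The protocol gives neither. With gains spread evenly, a clear difference remains at m = 10 or 20. This stands: the effect is dilution of unknown size.
- The Section 3 sub-group can be analysed whatever the primary definition is, and time to diagnosis and number of biopsies may also show benefit. This stands, but those analyses do not restore the lost pairs to the primary comparison.
- An MDT diagnosis may itself rest on tissue; Section 7.3 records that separately. Route iii could therefore mean an MDT conclusion drawn from a biopsy. The wording does not say so, and on that reading it would largely repeat routes i and ii.
- Deleting route iii without comment would leave it unclear when the standard pathway ends for MDT-only participants, because Section 10 lets a confirmed malignant diagnosis stop the pathway. This stands, and the fix must deal with it.

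**Conclusion.** The point holds in conditional form. The definition departs from its own label and leaves the tissue requirement, time point and pathway of route iii open. Over the whole pathway, the reading that fits the 30% standard rate, the route turns MDT-only participants into concordant pairs and biases the paired contrast towards zero. At the baseline biopsy it does nothing, or can favour only the proposed pathway. Neither reading gives it a useful role in the primary outcome.

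The size cannot be stated because m is not reported. The evenly spread illustration (22.0, 15.3 or 8.5 points left of 28.8) depends on the assumed m, on treating the planning rates as tissue-based and on one-way discordance. The loss is larger if gains concentrate in MDT-only participants. The protocol fixes this definition itself in two places, so it is not a detail left to a statistical analysis plan.

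**What to change.** In Section 10 and in the trial summary:

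1. Define the primary outcome by tissue criteria i) or ii) only, and name the biopsy on which it is scored.
2. Report MDT-only (clinico-radiological) diagnoses as a separate category in each pathway, using the Section 7.3 variable on whether the diagnosis was tissue based.
3. State that an MDT diagnosis still ends the pathway for the secondary outcomes: time to diagnosis, number of biopsies and number of MDT discussions.
4. If wanted, keep the outcome including route iii as a sensitivity analysis.

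The cost is a wording change, made before scoring begins, and a lower standard-pathway rate if the outcome would otherwise have been scored over the whole pathway. No new data are needed: the protocol already plans to extract the variables, from medical records where the trial database lacks them.

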7.5 End of trial

The trial will be completed when all samples have been stained and reported, with all pathology reporting queries answered.

8 Safety reporting

There is no new patient contact, intervention or sampling as part of REPLICA. There is therefore no safety reporting required.

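### Survival is listed for comparison between two pathways that share the same 59 people and one survival time each, so the contrast can only be a forced null or lead time

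*Protocol*

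**What the plan says.** Section 10 closes the list of secondary outcomes with "biopsy-associated costs, biopsy-related adverse events and survival". It defines the exposure: "The independent variable is the availability of BAP1, p16 FISH and MTAP testing", coded yes or no. Outcome measures are to be tabulated and compared for the two pathways, and "The relationship between secondary outcomes and availability of the tests will be evaluated using adjusted and unadjusted regression analyses and time to event analysis", the latter by a Cox model. Survival is not exempted from either sentence.

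The groups are defined in the same section: "Each participant will be assessed as a case (proposed pathway) and as an internal control (standard pathway) generating two groups of 59 = 118 records". Section 4 describes the design the same way, with each participant also serving as "internal control (initial outcomes using standard testing only". The safety reporting section adds: "There is no new patient contact, intervention or sampling as part of REPLICA". Section 7.2 expects the patients to have died by the time of the study.

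Section 7.3 extracts overall survival from the historic record and gives it no time origin. The only origin stated there is enrolment, for time to diagnosis. The secondary outcomes in the trial summary table (Section iii) stop at "vi) Biopsy-related adverse events" and do not include survival. Section 3 sends the reader to that table for the outcomes.

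**The concern.** A comparison of survival between pathways needs survival under both. Here the proposed pathway is a relabelling of stored samples: a marker result obtained now may change when a diagnosis would have been made, but it cannot change when the person died. Survival under the proposed pathway is therefore unobserved, and the protocol describes no model for it.

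Either possible result could mislead. A hazard ratio of 1 could be read as evidence that earlier diagnosis does not lengthen life, when the data cannot speak to that. A hazard ratio below 1 could be read as confirming the expectation in Section 1 that earlier diagnosis improves the chances of survival, when it would be an artefact of moving the starting point. Because the fault lies in pairing this outcome with this design, a later choice of time origin or covariates does not remove it.

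**Working it through.** The protocol gives no effect size or precision for survival, so there is no planned figure to reproduce. The check is whether any calculation from the planned data could be informative.

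**Inputs from the protocol.** 59 participants, each contributing one standard and one proposed record, 118 in all (Section 10); no new intervention (safety reporting section); one historic overall survival per person (Section 7.3); median survival in pleural mesothelioma of 9 to 12 months (Section 1), used only to set a scale.

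**Assumptions, because the documents do not give them.** The share *f* of participants whose diagnosis moves earlier (30% or 50%) and the lead *L* in those participants (1, 2 or 3 months).

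**Step 1: common origin.** For participant *i*, let E be the enrolment date and T the death date. Survival is T − E in both records. At each death time the two records of one person fail together, one in each group, and the risk set holds equal numbers from each group. At log HR = 0 the expected number of failures in the proposed group is 2 × ½ = 1 and the observed number is 1, so the score is 1 − 1 = 0 at every death time. The estimate is therefore log HR = 0, HR = 1. Fitting a Cox model to 59 simulated exponential times entered twice (medians 9, 10.5 and 12 months) gave HR = 1.0 and p = 1.0 each time, with and without censoring at 12 months.

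**Step 2: origin at each pathway's own diagnosis date.** Let D_S and D_P be the standard and proposed diagnosis dates. The within-person difference is

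(T − D_P) − (T − D_S) = D_S − D_P = lead time.

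The death date cancels. The expected gain over the cohort is *f* × *L*: at the low end 0.3 × 1 = 0.3 months, at the high end 0.5 × 3 = 1.5 months.

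**Step 3: what a Cox model would show in Step 2.** Mean HR over 300 simulated cohorts of 59 per row, with exponential survival and every death observed and unchanged:

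| Share moved | Lead (months) | Expected gain *f* × *L* (months) | HR, median 9 months | HR, median 12 months |
|---|---|---|---|---|
| 30% | 1 | 0.3 | 0.962 | 0.967 |
| 30% | 2 | 0.6 | 0.940 | 0.952 |
| 30% | 3 | 0.9 | 0.920 | 0.933 |
| 50% | 1 | 0.5 | 0.938 | 0.947 |
| 50% | 2 | 1.0 | 0.903 | 0.921 |
| 50% | 3 | 1.5 | 0.870 | 0.897 |

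Every departure from 1 in this table is lead time.

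**Step 4: adjustment.** Section 10 proposes to adjust, where possible, for age, sex, biopsy method and tumour histology. In Step 1 there is no difference to adjust. In Step 2 the death date has already cancelled, so no covariate can turn the remaining lead time into a survival effect.

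**The case against.** The strongest reply is that survival hardly figures in this plan. It is one word at the end of a list, absent from the objectives in Section 3 and from the trial summary table. The rationale in Section 2 rests on earlier diagnosis, fewer biopsies and cost. The generic Cox sentence fits time to diagnosis naturally, and no dedicated survival model is specified. The only time origin in the document is enrolment, so the likelier outcome is an evidently empty null rather than a false benefit. All of this stands, and it lowers the severity. It does not rescue the comparison: Section 10 applies the pathway contrast to the secondary outcomes without exception, and no origin makes it informative.

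It can also be said that some survival times may be censored, since follow-up in the parent trial was 12 months. That is fair, but a censored time is duplicated like any other and Step 1 is unaffected.

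Two stronger readings are tempting and not supported.

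- A reader might infer that stage fails in the same way. It does not. Section 7.3 extracts biopsy dates and the imaging from the diagnostic period, so stage at an earlier biopsy could be read from imaging of that time. Stage is not null by construction. What the protocol lacks is a rule for assigning it, which may sit in an analysis plan not seen here.
- A reader might take a 2-month lead for everyone and quote an apparent gain of 2/12 = 17% to 2/9 = 22%. That requires every participant's diagnosis to move. Only those with a qualifying marker result on an earlier biopsy would move, and the cohort has suspected malignancy, so some may not have mesothelioma. The 9 to 12 months is also background for the disease, not this cohort's survival.

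**Conclusion.** The point holds for survival as a between-pathway outcome. From a common origin the hazard ratio is exactly 1. From pathway-specific diagnosis dates the difference is lead time alone, for illustration a mean of 0.3 to 1.5 months and an HR of about 0.87 to 0.97. Those figures rest on the assumed shares and leads and on exponential survival; the conclusion does not. It needs only that each person has one survival time and that the proposed pathway was not delivered, both of which follow from the protocol.

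The documents do not show that the investigators intend to measure survival from diagnosis, so it would go too far to say that the plan will report a spurious benefit. Severity is should-fix: the primary outcome, the sample size and the named objectives do not depend on survival. The disagreement between the Section 10 list and the trial summary table is real but editorial.

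**What to change.** In Section 10:

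- Remove survival from the outcomes compared between pathways.
- State that the Cox model applies to time to diagnosis only.
- Report overall survival once, descriptively, for the whole cohort from a stated common origin such as enrolment.
- Align the list of secondary outcomes with the trial summary table, which omits survival.

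Stage is a separate and lesser matter. The comparison can stay if the plan says that proposed-pathway stage is assigned from imaging at the earlier biopsy date, not copied from the stage at actual diagnosis.

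The cost is protocol wording. One pathway contrast that could not be informative is lost, and no data collection changes, since overall survival and the diagnostic imaging are already to be extracted. If the stage comparison is kept, reading stage from the earlier imaging adds some work.
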